3.8.2 Secondary Efficacy

Key Secondary Objective

The key secondary objective of this study is to estimate the hazard ratio of a PFS event using local investigator's/radiologist's tumor assessments comparing the everolimus + exemestane

combination therapy with the capecitabine therapy in postmenopausal women with ER-positive, HER2-negative, advanced breast cancer after recurrence or progression on letrozole or anastrozole.

The stratified Cox regression model will be used to estimate the hazard ratio of a PFS event, along with the associated 90% confidence interval, comparing the everolimus + exemestane combination therapy with the capecitabine therapy where the stratification information will be obtained through IRT. The confidence interval for the hazard ratio will not be adjusted for multiple comparisons.

Distribution of PFS will be assessed using the Kaplan-Meier estimation method. The estimated median PFS for each treatment group will be provided along with the approximate 90% confidence intervals. Additionally, the 25th and 75th percentiles will also be computed. The progression-free survival probabilities at 2, 4, 6 and 9 months (timepoints to be adapted depending on the length of the follow-up), along with 90% confidence intervals, will be presented by treatment group.

The same statistical principles will be applied and supportive analyses conducted as described in [Section 3.8.1](#) “Sensitivity and other supportive analyses of the primary endpoint PFS” for the key secondary treatment comparison of everolimus + exemestane combination therapy versus capecitabine therapy.

Other Secondary Objectives

Other secondary objectives of this study are to evaluate each of everolimus + exemestane versus everolimus monotherapy and everolimus + exemestane versus capecitabine monotherapy with respect to overall survival (OS), overall response rate (ORR), clinical benefit rate (CBR), deterioration in the ECOG performance status, changes in quality of life scores over time, and safety.

The analysis of all secondary efficacy endpoints (mentioned above) will be performed on the FAS.

Overall survival (OS)

Overall survival (OS) is defined as the time from the date of randomization to the date of death due to any cause. The cut-off date for the planned final OS analysis was specified 2 years after the randomization of the last patient. However, at that time, the number of PFS events needed for final PFS analysis was not reached. Therefore the final OS analysis will be conducted at the time of the planned final PFS analysis using the same cut-off date. If death has not been observed by the analysis cut-off date, then OS will be censored at the date of last contact.

The OS analysis will be based on data from the FAS on the ITT basis, i.e., according to the treatment group patients are randomized to at baseline. Distribution of OS in each of the three treatment arms will be assessed using the Kaplan-Meier (KM) estimation method, and the treatment-specific KM curves will be graphically displayed. The estimated median OS and probability of surviving at the estimated median OS, along with 90% confidence intervals, will be presented for the three treatment arms. Stratified Cox regression models will be used to estimate the hazard ratio (HR) of death from any cause, along with the associated 90%

confidence interval, comparing (i) the everolimus + exemestane combination therapy with everolimus monotherapy, and (ii) the everolimus + exemestane combination therapy with capecitabine therapy where the stratification information will be obtained through IRT and the baseline hazard functions will be allowed to vary across strata.

As a sensitivity analysis, a stratified multivariate Cox regression model will be fitted after additional adjustment for key potential prognostic factors including prior chemotherapy (yes vs. no), performance status (0 vs. 1, 2), presence of bone lesions only at baseline (yes vs. no), time since first diagnosis of metastasis/recurrence to randomization (<6 Months, ≥ 6 Months), non-steroidal aromatase inhibitor (NSAI) (letrozole or anastrozole) usage (adjuvant vs. metastatic), number of organs involved (1 vs. 2 vs. ≥ 3 – to be adapted depending on the number of patients in each category) and PgR status (positive vs. negative). A revised multivariate stratified cox model including the key prognostic factors as well as the baseline covariates where imbalances between arms have been observed will be added: performance status (0 vs. 1 or 2), presence of bone lesions only at baseline (yes vs. no), number of organs involved (1 vs. 2 vs. ≥3), prior chemotherapy use (yes vs. no), age (<65 years vs. ≥65 years old) and Race (Caucasian vs. non-caucasian). The strata will be based on stratification information obtained through IRT.

Survival status, reason for censoring and death cause will be listed. Patients not known to have died will be censored for ‘Lost to follow-up’ if the time between their last contact date and the analysis cut-off date is longer than 3 months and 2 weeks (104 days).

95% confidence intervals for the median, hazard ratio and survival probabilities of the overall survival will be also provided as supportive analysis.

Overall response rate (ORR)

Overall response rate (ORR) is defined as the proportion of patients with best overall response of complete response (CR) or partial response (PR) according to RECIST 1.1 ([Appendix 1](#)). ORR will be calculated based on the FAS according to the ITT principle, using local radiologist’s/investigator’s tumor assessment. Patients with bone lesions only at baseline will be included in the numerator if they achieve a complete response. ORR estimates will be presented by treatment group along with exact 90% confidence intervals ([Clopper and Pearson 1934](#)). The estimation procedure will be repeated based on data for a subset of patients in the FAS with measurable disease only at baseline.

Clinical benefit rate (CBR)

Clinical benefit rate (CBR) is defined as the proportion of patients with best overall response of CR, PR, or overall lesion response of stable disease (SD for measurable disease and non-CR/non-PD (NCRNPD) for non-measurable disease) with duration of 24 weeks or longer. A patient will be considered to have a SD/NCRNPD for 24 weeks or longer if SD/NCRNPD is recorded at 24 weeks or later after randomization. Taking into account the allowed time window for tumor assessment visits, the SD/NCRNPD response has to be recorded at 23 weeks or later after randomization to be included in the CBR calculation. Best overall

response of CR, PR and overall lesion response of SD/NCRNPD are defined according to RECIST 1.1 (see Appendix 1). CBR will be calculated based on the FAS according to the ITT principle, using local radiologist’s/investigator’s tumor assessment. Patients with non-measurable disease only at baseline will be included in the numerator if they achieve a complete response. CBR estimates will be presented by treatment group along with exact 90% confidence intervals.

ECOG performance status

ECOG performance status (PS) scale will be used to assess physical health of patients, ranging from 0 (most active) to 5 (least active):

Table 3-1 ECOG Performance Status Scale

Score	Description
0	Fully active, able to carry on all pre-disease performance without restriction
1	Restricted in physically strenuous activity but ambulatory and able to carry out work of a light or sedentary nature, e.g., light house work, office work
2	Ambulatory and capable of all self-care but unable to carry out any work activities. Up and about more than 50% of waking hours
3	Capable of only limited self-care, confined to bed or chair more than 50% of waking hours
4	Completely disabled. Cannot carry on any self-care. Totally confined to bed or chair
5	Dead

ECOG performance status will be assessed and recorded at baseline, on Treatment Day 1, at week 6 and every 6 weeks thereafter as well as at discontinuation from the study treatment (within one week after discontinuation). If patients discontinue study treatment for any reason other than progression, lost to follow-up or consent withdrawal, the ECOG performance status will continue to be performed every 6 weeks until progression, lost to follow-up, consent withdrawal or investigator decision in patient best interest.

Time windows will be defined for summaries of ECOG data. If more than one assessment is available in the same time window, the assessment closest to the planned date will be considered. If two assessments are obtained with the same time difference compared to the scheduled visit day, the assessment with the worst value will be considered. Data obtained at the end of treatment will be classified as other assessment in the corresponding time window. Note that only data collected under treatment (i.e. while the patient is treated and up to 7 days after last dose intake) will be included in the time to deterioration analysis. Post-treatment data will be summarized separately. The end of treatment assessment will be included if collected within 7 days of the last dose intake.

Time Window	Planned visit timing	Time Window Definition
Baseline	On or before Study Day 1	<= Study Day 1
Week 6	Study Day 43	Study Days 22-63

Week 12	Study Day 85	Study Days 64-105
Week 18	Study Day 127	Study Days 106-147
Every 6 weeks thereafter, Week $y=18+6*k$ (with $k=1,2 \dots$)	Study Day $(18+6*k)*7+1$	Study Days $(18+6*k)*7-20$ to $(18+6*k)*7+21$ Note: EOT data visit are included if obtained within 7 days of last non-0 dose intake.
Study Day 1 = randomization date		

Frequencies of patients with ECOG PS values of 0, 1 or ≥ 2 will be used to summarize the ECOG PS data at each time window. .

An analysis of the time to definitive deterioration of the ECOG PS by at least one category of the score from baseline will be performed. A deterioration will be considered definitive if no improvements in the ECOG PS are observed at subsequent measurement times during the treatment period following the time point at which the deterioration is observed. (Example 1: if the score is 1 at baseline and then 1, 2, 1, 2, 3 at study days 28, 57, 83, 115, 150, respectively, then the time to definitive worsening is 115 days. Example 2: if the score is 1 at baseline and then 1, 1, 2 at study days 28, 57, 83, respectively, with no assessment of the ECOG performance status after day 83, then the time to definitive worsening is 83 days.)

Death will be considered as worsening of the ECOG PS if it occurs close to the last available assessment where “close” is defined as being within twice the planned period between two assessments. Patients who die after more than twice the planned period between two assessments will be censored at the date of their last assessment before the cut-off. This avoids overestimating the time to definitive worsening in patients dying after an irregular assessment scheme. For example, if the last assessment is at week 6 and the patient dies at week 16, the definitive deterioration date will be week 16. On the other hand, if the last assessment is at week 6 and the patient dies at week 22, which is after more than twice the planned period between two assessments (6 weeks) since the last assessment (at week 6), then the patient is censored for definitive deterioration and the censoring date will be week 6. Patients receiving any further anti-neoplastic therapy prior to definitive worsening will be censored at their date of last assessment prior to the start of therapy. Patients that have not worsened at the data cut-off point will be censored at the date of last assessment prior to the cutoff.

The Kaplan-Meier estimation method will be used to assess the distribution of time to definitive worsening in the ECOG PS score, stratified by treatment. The estimated treatment-specific median times to definitive worsening will be presented along with 90% confidence intervals. The stratified Cox regression model will be used to estimate the hazard ratio of a definitive worsening in the ECOG PS score, along with the associated 90% confidence interval, comparing the everolimus + exemestane combination therapy with everolimus alone and comparing the everolimus + exemestane combination therapy with the capecitabine therapy.

Patient reported outcomes (PRO)

The FAS will be used for all PRO summaries and listings.

Quality of life questionnaire (QLQ)

The EORTC QLQ-C30 questionnaire along with the breast module (BR23) will be used to collect patients' quality of life (QoL) data. Raw QoL data will be scored according to the EORTC scoring manual. If at least half of the items comprising the scale have been answered, the score for this scale will be calculated. For single item scales with missing responses and scales where less than half of the items have been answered, the score for these scales will be set to missing. The global health status/QoL scale score is identified as the primary QoL variable of interest. Physical functioning, emotional functioning and social functioning scale scores in QLQ-C30, and functional and symptom scale scores in BR23 are identified as secondary QoL variables of interest.

QLQ-C30 and BR23 will be assessed and recorded at baseline, on Treatment Day 1, at week 6 and every 6 weeks thereafter as well as at discontinuation from the study treatment (within one week after discontinuation). If patients discontinue study treatment for any reason other than progression, lost to follow-up or consent withdrawal, the QLQ-C30 and BR23 performance status and will continue to be performed every 6 weeks until progression, lost to follow-up, consent withdrawal or investigator decision in patient best interest.

Time windows will be defined for descriptive summaries of PRO data. If more than one assessment is available in the same time window, the assessment closest to the planned date will be considered. If two assessments are obtained with the same time difference compared to the scheduled visit day, the assessment obtained prior to scheduled visit day will be considered. Data obtained at the end of treatment will be classified as other assessment in the corresponding time window. Note that only data collected under treatment (i.e. while the patient is treated and up to 7 days after last dose intake) will be included in the time to deterioration analysis. Post-treatment data will be summarized separately. The end of treatment assessment will be included if collected within 7 days of the last dose intake.

Time Window	Planned visit timing	Time Window Definition
Baseline	On or before Study Day 1	<= Study Day 1
Week 6	Study Day 43	Study Days 22-63
Week 12	Study Day 85	Study Days 64-105
Week 18	Study Day 127	Study Days 106-147
Every 6 weeks thereafter, Week $y=18+6*k$ (with $k=1,2 \dots$)	Study Day $(18+6*k)*7+1$	Study Days $(18+6*k)*7-20$ to $(18+6*k)*7+21$ Note: EOT data visit are included if obtained within 7 days of last non-0 dose intake.

Study Day 1 = randomization date

The number of patients filling QoL data and the number of patients missing/expected to have QoL assessments will be summarized by each treatment group for scheduled assessment time points. Furthermore, the amount and the pattern of missing data will be explored by treatment group and over time. The following categories will be used to describe whether the questionnaire was completed at a specific time point:

- yes, fully completed
- yes, partially completed
- no, patient (or subject) missed scheduled assessment visit
- no, patient refused due to poor health
- no, patient (or subject) refused (unrelated to health)- no, study staff felt patient was too ill
- no, questionnaire not available
- no, institutional error
- no, other

Other exploratory analyses may be performed to better understand the missingness pattern for QoL data.

Descriptive statistics (count, mean, median, standard deviation, first and third quartile) will be used to summarize domains at each scheduled assessment time. Patients will be included if they completed at least one questionnaire item. Additionally, change from baseline in the scale scores at the time of each assessment will be summarized. Patients with an evaluable baseline score and at least one evaluable post-baseline score during the treatment period will be included in the change from baseline analysis.

Time to definitive 10% deterioration in the global health status / QoL score, and in each of the three secondary scales, will be examined for the three treatment arms. In addition, time to definitive 5-point and 10-point deterioration in the global health status / QoL score will be explored for each treatment arm. The assessed distributions will be presented descriptively using Kaplan-Meier curves. Summary statistics based on Kaplan-Meier distributions will be presented, including the estimated median time to definitive 10% (5-, 10-point) deterioration and the probability of not experiencing definitive 10% (5-, 10-point) deterioration by 12 and 24 weeks. Both point estimates and 90% confidence intervals will be presented.

Definitive 10% (5- or 10-point) deterioration is defined as a decrease in score by at least 10% (5 or 10 points) compared to baseline, with no later increase above this threshold observed during the course of the study. Baseline is defined as the latest available assessment made on or before the date of randomization when patient can still deteriorate. Time to definitive deterioration is the number of days between the date of randomization and the date of the assessment at which definitive deterioration is seen.

Death will be considered as deterioration of symptoms/QoL if it occurs close to the last available assessment where “close” is defined as twice the planned period between two assessments. This avoids overestimating the time to definitive worsening in patients dying after an irregular assessment scheme. Patients who die after more than twice the planned

period between two assessments since the last assessment will be censored at the date of their last available questionnaire.

Patients receiving any further anti-neoplastic therapy before definitive worsening will be censored at the date of their last assessment before starting this therapy. Patients that have not worsened as of the cut-off date for the analysis will be censored at the date of their last assessment (questionnaire) before the cut-off.

Treatment satisfaction questionnaire for medication (TSQM)

Patients' self-reported satisfaction or dissatisfaction with the study treatment will be measured using the Treatment Satisfaction Questionnaire for Medication (TSQM) version 1.4. TSQM is planned to be administered at week 3, 6, 12, and the end-of-treatment (EOT) visit. The questionnaire will be administered in the patients' local language.

TSQM items will be divided into four scales: side effects, effectiveness, convenience, and global satisfaction. Raw TSQM data will be scored according to the scoring manual. Only scale scores with not more than one missing item will be computed.

The following time-based intervals will be used to group TSQM data over time. Day x is defined as date of TSQM administration – randomization date + 1. If more than one assessment is available in the same time window, the assessment closest to the planned date will be considered. If two assessments are obtained with the same time difference compared to the scheduled visit day, the assessment obtained prior to scheduled visit day will be considered.

Time window	Planned visit timing	Time Window Definition
Week 3	Study Day 22	Days 11 to 31
Week 6	Study Day 43	Days 32 to 63
Week 12	Study Day 85	Days 64 to 105
EOT	EOT Day	Days (EOT-20) to (EOT+7)

If EOT occurs at the same time of week 3, week 6 or week 12 time window, priority is given for reporting at EOT time window.

[figure not shown]
All summaries of TSQM data will be based on the FAS according to the ITT principle. The number of patients filling TSQM data and the number of patients missing/expected to have TSQM assessments will be summarized by each treatment group for scheduled assessment time points. Furthermore, the amount and the pattern of missing data will be explored by treatment group and over time. The following categories will be used to describe whether the questionnaire was completed at a specific time point:

[figure not shown]
- yes, fully completed
- yes, partially completed

- no
- no, patient (or subject) missed scheduled assessment visit
- no, patient refused due to poor health
- no, patient (or subject) refused (unrelated to health)
- no, study staff felt patient was too ill
- no, questionnaire not available in the appropriate language
- no, institutional error
- no, other

Other exploratory analyses may be performed to better understand the missingness pattern for TSQM data.

Descriptive statistics (count, mean, median, standard deviation, first and third quartile) will be used to summarize individual item and multi-item scale scores by treatment group and assessment time point (week 3, week 6, week 12, and EOT). Differences in mean scale scores at weeks 3 and 12, and differences in mean change in scale scores between weeks 3 and 12 along with 90% confidence intervals comparing treatment satisfaction with everolimus + exemestane versus everolimus alone, and everolimus + exemestane versus capecitabine will be reported (no significance testing will be performed). The normal approximation will be used in the computation of confidence intervals.

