### Notes:

- Lymph nodes have to be  $\geq 15$  mm in short axis to be considered measurable
- If bone lesions have been previously irradiated, at least one lesion must have clearly progressed since the radiotherapy by CT, MRI or x-ray for trial entry (in absence of measurable disease)

Clinical lesions (i.e., skin nodules and palpable lymph nodes) will only be considered measurable when they are superficial. For the case of skin lesions, documentation by color photography, including a ruler to estimate the size of the lesion, is recommended.

Lytic bone lesions or mixed lytic-blastic lesions, with identifiable soft tissue components, should not be considered as a measurable lesion in this trial. Blastic bone lesions are nonmeasurable. These lesions should be captured as non-target lesions on the appropriate eCRF page(s).

In the absence of measurable disease at baseline, patients with bone only lesions (lytic + blastic) will be allowed to enter the study and the following will be considered disease progression among these patients:

- the appearance of one or more new lytic lesions in bone
- the appearance of one or more new lesions outside of bone
- unequivocal progression of existing bone lesions.

Please refer to Appendix 1 for details regarding the evaluation of response criteria.

**Note:** If an initial observation of response is made, a confirmation scan (or photography for measurable skin lesions) should be obtained at least 4 weeks after the initial observation.

Table 7-2 Imaging/RECIST Assessment Collection Plan

Procedure	Screening/Baseline	During Treatment/Follow-up			
CT or MRI (Chest, Abdomen, Pelvis)	Mandated	Mandated, every 6 weeks (+/- 7 days).			
Whole body bone scan or skeletal survey	Mandated	If clinically indicated			
Brain CT or MRI (e.g. Brain)	Mandated if symptoms suggestive of CNS metastases present	If clinically indicated			
Bone X-ray (or CT / MRI)	Mandated during screening period for any hot spot or positive finding identified by bone scan/skeletal survey to confirm bone lesion(s)	Mandated for any confirmed bone lesion at screening every 6 weeks (+/- 7 days). The same method used at screening (for confirmation) should be used at each evaluation.  Mandated for any hotspot or positive finding identified by bone scan/skeletal survey during treatment/follow up.			
Color photography (with a ruler)	Mandated for any skin lesions at screening	Mandated for any skin lesions identified at screening every 6 weeks			

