#### 10.5.2.3 Clinical Benefit Rate (CBR)

Clinical Benefit Rate (CBR) is defined as the proportion of patients with best overall response of CR, PR or stable disease (SD) with duration of 24 weeks or longer. A patient will be considered to have a SD for 24 weeks or longer if SD is recorded at 24 weeks or later after randomization. Taking into account the allowed time window for tumor assessment visits, the SD response has to be recorded at 23 weeks or later after randomization to be included in the CBR calculation. CR, PR and SD are defined according to RECIST 1.1 (see Appendix 1).

CBR will be calculated based on the FAS according to the ITT principle, using local radiologist's/investigator's tumor assessment. Patients with non-measurable disease only at baseline will be included in the numerator if they achieve a complete response. CBR will be summarized for the three treatment groups using descriptive statistics.

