- PR = at least two determinations of PR or better at least 4 weeks apart before progression (and not qualifying for a CR) where confirmation required or one determination of PR prior to progression where confirmation not required

- SD = at least one SD assessment (or better) > 6 weeks after randomization/start of treatment (and not qualifying for CR or PR).
- PD = progression  $\leq$  12 weeks after randomization/ start of treatment (and not qualifying for CR, PR or SD).
- UNK = all other cases (i.e. not qualifying for confirmed CR or PR and without SD after more than 6 weeks or early progression within the first 12 weeks)

Overall lesion responses of CR must stay the same until progression sets in, with the exception of a UNK status. A patient who had a CR cannot subsequently have a lower status other than a PD, e.g. PR or SD, as this would imply a progression based on one or more lesions reappearing, in which case the status would become a PD.

Once an overall lesion response of PR is observed (which may have to be a confirmed PR depending on the study) this assignment must stay the same or improve over time until progression sets in, with the exception of an UNK status. However, in studies where confirmation of response is required, if a patient has a single PR (≥30% reduction of tumor burden compared to baseline) at one assessment, followed by a <30% reduction from baseline at the next assessment (but not  $\geq 20\%$  increase from previous smallest sum), the objective status at that assessment should be SD. Once a confirmed PR was seen, the overall lesion response should be considered PR (or UNK) until progression is documented or the lesions totally disappear in which case a CR assignment is applicable. In studies where confirmation of response is not required after a single PR the overall lesion response should still be considered PR (or UNK) until progression is documented or the lesion totally disappears in which case a CR assignment is applicable.

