2.5.3 Best overall response

The best overall tumor response will be assessed per RECIST 1.1. The definitions and details of the derivation are given in [\[Appendix 1 of the study protocol\]](#).

Only tumor assessments performed before the start of any further anti-neoplastic therapies (i.e., any additional anti-neoplastic medications or surgery) will be considered in the assessment of best overall response. These anti-neoplastic therapies will be identified from the data collected on ‘Anti-neoplastic therapies since discontinuation of study drug’ eCRF.

Since, in this study, tumor assessments are performed every 6 weeks, allowing for a ± 1 -week deviation window, the standard definition of a best overall response evaluation of “stable disease”, “progressive disease” or “unknown” given in [\[Appendix 1 of the study protocol\]](#) requires an adjustment.

The following definitions will be used:

- The determination of CR and PR remains the same as stated in [\[Appendix 1 of the study protocol\]](#).
- SD = at least one SD assessment (or better) after randomization (and not qualifying for CR or PR). Because the first assessment after randomization is scheduled at 6 weeks, allowing for a 1-week deviation window, SD is defined as at least one SD assessment (or better) > 5 weeks after randomization (and not qualifying for CR or PR).
- If progression is detected as the first evaluable assessment in ≤ 9 weeks after randomization, the best overall response evaluation will be “progressive disease.”
- UNK = all other cases (i.e., not qualifying for confirmed CR or PR and without SD for more than 5 weeks or early progression within the first 9 weeks).

Patients with best overall response “unknown” will be summarized by reason for having unknown status. The following reasons will be used:

- no valid post-randomization assessment,
- all post-randomization assessments have overall response UNK,

- new anti-neoplastic therapy started before first post-randomization assessment,
- SD in less than 5 weeks post-randomization ('SD too early'),
- PD after more than 9 weeks post-randomization ('PD too late').

Special (and rare) cases where best overall response is "unknown" due to both SD in less than 5 weeks and PD after more than 9 weeks post-randomization will be classified as 'SD too early.'

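### If responses must be confirmed, the clinical benefit rule counts SD at week 24 but not an unconfirmed first PR or CR at the same visit

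*SAP*

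**What the plan says.** SAP 3.8.2 gives two routes into the CBR numerator. Route 1 is a best overall response of CR or PR. Route 2 works on the response at a single visit: "or overall lesion response of stable disease (SD for measurable disease and non-CR/non-PD (NCRNPD) for non-measurable disease) with duration of 24 weeks or longer". After allowing for the visit window, it requires that "the SD/NCRNPD response has to be recorded at 23 weeks or later after randomization to be included in the CBR calculation".

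Protocol 10.5.2.3 sets the same timing condition: "the SD response has to be recorded at 23 weeks or later after randomization to be included in the CBR calculation". It differs in treating SD as a category of best overall response, not of one visit's response.

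For best overall response, SAP 2.5.3 words the SD criterion more generously: "SD is defined as at least one SD assessment (or better) > 5 weeks after randomization".

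On confirmation, the documents say the following:

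- SAP 2.5.3 describes the residual UNK class as "not qualifying for confirmed CR or PR and without SD for more than 5 weeks".
- Protocol 4.1.2 and 7.2.1.1 ask for a confirmation scan no sooner than four weeks after a first response.
- Where confirmation applies, Protocol 14.1.17 says "PR = at least two determinations of PR or better at least 4 weeks apart before progression".
- Protocol 14.1.17 also treats confirmation as optional outside two kinds of trial (non-randomized trials with response as primary endpoint, and trials for accelerated approval).
- No section states outright whether CR and PR must be confirmed in this study.

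**The concern.** Route 2 has no *or better*, and a PR visit cannot stand in for an SD visit. Protocol Table 14-1 defines target-lesion SD so as to exclude shrinkage that meets PR or CR, and Table 14-3 lists PR and SD as separate visit responses. An isolated PR or CR at week 24 can therefore miss both routes: it is not confirmed, so Route 1 fails, and it is not SD, so Route 2 fails.

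A better scan then lowers the endpoint, which no sensible meaning of clinical benefit supports. What is at stake is the correct classification of a few patients in each arm's CBR.

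**Working it through.** **Inputs.**

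- Scans, Protocol Table 7-2: "Mandated, every 6 weeks (+/- 7 days", hence weeks 6, 12, 18, 24 and 30.
- CBR duration of 24 weeks (SAP 3.8.2).
- Two determinations at least 4 weeks apart where confirmation applies (Protocol 14.1.17).
- 309 patients randomized (Protocol, Amendment 3); 300 planned, 1:1:1.

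**Step 1: the plan's own threshold.** 24 weeks − 1 week window = 23 weeks. It reproduces.

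**Step 2: the literal rule on single histories.** All have SD at weeks 6, 12 and 18, and confirmation is assumed to be required.

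| Week 24 | Week 30 | Best overall response | CBR as written | CBR with *or better* |
|---|---|---|---|---|
| SD | PD | SD | yes | yes |
| PR | PD | SD | **no** | yes |
| PR | UNK | SD | **no** | yes |
| PR | no scan | SD | **no** | yes |
| PR | SD | SD | yes | yes |
| PR | PR | PR | yes | yes |

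If one PR is enough for best overall response, every PR row has best overall response PR and counts as written.

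**Step 3: all histories.** Take PR, SD, PD or UNK at each of five visits and stop at the first PD. The number of distinct sequences is (1 + 3 + 9 + 27 + 81) + 243 = 364.

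- With confirmation required, adding *or better* changes 24 of them. Each of weeks 6, 12 and 18 is SD or UNK, giving 2 × 2 × 2 = 8 starts. The endings are PR then PD, PR then UNK, or UNK then PR, giving 8 × 3 = 24.
- All 24 have a single PR, at week 24 or 30, and no SD visit at or after week 23.
- With confirmation not required, 0 change.

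These are counts of patterns, not probabilities. An isolated CR at week 24 falls into the same gap.

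**Step 4: which events can cause it.**

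- *Progression, new therapy, or no further adequate assessment* after the first response: yes. SAP 2.5.3 uses only assessments before further anti-neoplastic therapy for best overall response.
- *Data cut-off*: no. The last patient was randomized on 24-Nov-2014 (Protocol, Amendment 3), and SAP 3.8.2 places the final cut-off later than 2 years after that. Each patient's week 24 was therefore at least 104 − 24 = 80 weeks before cut-off.
- *One missed scan alone*: no. The two determinations need not be consecutive visits; the worked example in Protocol 14.1.17 (PR, SD, PR) is a confirmed PR. PR, missing, PR is confirmed, and PR, missing, SD counts by Route 2.

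**Step 5: size.** One patient is 1/100 = 1.0 point on the planned arm size, or 1/103 = 0.97 point if the 309 are split equally. For an assumed 0 to 3 patients per arm, the shift is 0 to 3 points. For scale, at an assumed 45 of 100 the exact 90% CI is 36.5% to 53.7%, a half-width of (53.7 − 36.5)/2 = 8.6 points. At 48 of 100 it is 39.4% to 56.7%.

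**The case against.** The strongest objection is that the premise is never stated. This is a randomized trial with PFS as primary endpoint, so it falls in the group for which Protocol 14.1.17 calls confirmation optional. SAP 2.5.3 leaves the determination of CR and PR as in that appendix. The reference to confirmed responses sits in a gloss on UNK and follows the appendix's template wording. The confirmation-scan instruction concerns imaging, not derivation. This stands to the extent that the finding must be conditional. It does not dispose of it, because the study-specific texts all point towards confirmation and a programmer would have reason to apply it.

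A second objection is that *or better* can be read in by cross-reference. Protocol 10.5.2.3 uses SD as a best-overall-response category, which Appendix 1 defines as SD or better, and the appendix's duration of stable disease (Protocol 14.1.23) covers CR, PR and SD together. This is a fair reading of the protocol's 24-week criterion. It is weaker for the SAP, which governs the derivation, because the SAP refers to the overall lesion response at a visit.

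A third objection is that few patients qualify, and that stands. A patient with SD at week 24 and a first PR later already counts, and after an isolated PR a later SD visit rescues the patient.

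**Conclusion.** The rule gives a perverse result if CR and PR must be confirmed. It affects patients who meet all three conditions:

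- the first PR or CR is at about the week-24 visit, or later if earlier visits from week 23 on were missing or UNK;
- the response is not confirmed;
- there is no SD/NCRNPD visit at or after week 23.

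Each such patient costs the arm about 1 percentage point. The documents do not give the number affected; 0 to 3 per arm is an assumption, so 0 to 3 points. If confirmation is not required, the effect is nil. CBR is an *other secondary* endpoint, summarized descriptively without testing, so this is a minor point.

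A reader might infer that every unconfirmed response from week 23 on is lost, or that data cut-off or a single missed scan is enough to cause it. Steps 3 and 4 show otherwise. A reader might also infer a bias between arms, because SAP Addendum 1 reports an imbalance in informative censoring between capecitabine and the combination and examines patients censored for new therapy. A difference in CBR is possible, but the documents give no figures on late unconfirmed responses by arm and do not show one.

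**What to change.** In SAP 3.8.2 and Protocol 10.5.2.3, define Route 2 as an overall lesion response of SD/NCRNPD or better (CR, PR, SD or NCRNPD) recorded at 23 weeks or later, before progression and before any new anti-neoplastic therapy. State in the same place whether CR and PR must be confirmed for best overall response.

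While editing, reconcile the SAP 3.8.2 sentence that admits patients with non-measurable disease only on achieving CR with the rule that also counts their NCRNPD.

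The cost is a few words in each document, one condition in the derivation program and a rerun of the CBR table. The SAP already carries an addendum dated after database lock, so record this as a post-lock clarification and report the number of patients reclassified in each arm.
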